2.1.4.3 Summary of Safety

The currently available safety data demonstrate that bempegaldesleukin is a generally well-tolerated immuno-oncology agent when administered to late stage cancer patients as monotherapy and in combination with other immunotherapies and chemotherapy. Bempegaldesleukin has also been shown to be generally well-tolerated in cancer patients aged ≥ 60 years. The most common AEs include Grade 1 and 2 flu-like symptoms, including fever, chills/rigors, and influenza-like illness, which occur within a predictable time frame, approximately 1 to 4 days post-dose, and typically resolve spontaneously or are mitigated by nonprescription oral or topical treatments. These, along with rash, are managed with NSAIDS, acetaminophen, and antihistamines.

Hypotension, a known AE associated with both IL-2 and engineered cytokines, has been characterized as an identified risk of bempegaldesleukin. Instances of hypotension coincide with the peak plasma concentration of the active pegylated IL-2 conjugates formed after administration of bempegaldesleukin (NKTR-214-AC). Hypotension can be mitigated using the hydration management guideline, which has successfully reduced the frequency and severity of instances of hypotension in ongoing bempegaldesleukin studies and patients with bempegaldesleukin-induced hypotension are usually rapidly responsive to fluid administration.

Given the encouraging clinical activity to increase lymphocytes and the manageable toxicity profile, the potential for direct benefit in patients warrants evaluation of bempegaldesleukin with standard of care for COVID-19.

2.2 Scientific Rationale for Study Design

This Phase 1b study is designed to identify the RP2D of bempegaldesleukin in patients with mild COVID-19 with the long-term aim to advance to future studies evaluating bempegaldesleukin in hospitalized patients with moderate COVID-19 who are lymphopenic and at greater risk for mortality.

2.2.1 Rationale for Placebo Control

To objectively assess the safety and disease measurement of bempegaldesleukin treatment for adults with mild COVID-19, this study will be randomized, double-blind, and placebo controlled.

All patients will also receive the standard of care treatment for mild COVID-19 determined by the Investigator or institution, which should follow the approved prescribing guidelines in the country.

2.2.2 Rationale for Endpoints

This study is the first evaluation of bempegaldesleukin in patients with mild COVID-19, therefore, a primary objective of the study is to evaluate the safety, tolerability, pharmacokinetics, and pharmacodynamics of bempegaldesleukin.

Another primary objective of the study is to identify the recommended Phase 2 dose (RP2D) of bempegaldesleukin in patients with mild COVID-19.

The final primary objective of the study is to assess the effect of bempegaldesleukin on the time course and extent of changes in absolute lymphocyte counts, as decreased levels of lymphocytes

have been associated with a fatal outcome in COVID-19 (Tan 2020a), and in Wuhan, China, 40% to 70% of hospitalized patients for COVID-19 had lymphopenia (Zhou 2020; Huang 2020; Tian 2020 [preprint]; Wang 2020). Increased levels of activated CD4+ and CD8+ T lymphocytes are observed in recovering patients (Qin 2020) and recovery from COVID-19 is accompanied by maintenance of lymphocyte counts and robust T cell activation. In patients with late-stage cancer, many who have compromised immune systems, a single IV infusion of bempegaldesleukin reliably elevated total lymphocyte counts at least 2-fold within one week after treatment in the vast majority of patients, regardless of age. Comparable increases were also observed after multiple successive treatment cycles. Hence, evaluating changes in absolute lymphocyte counts in patients with mild COVID-19 may be useful to assess the potential therapeutic benefit of bempegaldesleukin to improve the recovery time from the disease, shorten hospital stays, prevent respiratory decline, and decrease mortality from the infection in patients with more moderate COVID-19.

2.2.3 Duration of Treatment for Study Drug (Bempegaldesleukin or Placebo)

Study drug administration will be limited to a single dose administration and monitoring in the hospital or in-patient facility will occur for a minimum of 8 days (ie, from Day 1 [day of dosing] to at least Day 8).

Patients will receive study drug in a hospital or in-patient facility setting.

2.2.4 Justification for Dose of Bempegaldesleukin

The starting bempegaldesleukin dose of 0.00075 mg/kg will be administered as a single IV infusion over 15 (\pm 5) minutes in an initial cohort of 10 patients (5 bempegaldesleukin plus standard of care [referred to in this document as bempegaldesleukin/SOC] and 5 placebo plus standard of care [referred to in this document as placebo/SOC]). The range of doses that may be tested, 0.00075 to 0.003 mg/kg, is supported by data demonstrating the potential to be pharmacologically active with a low likelihood of the toxicity observed in studies of bempegaldesleukin in patients with cancer. This range is specifically supported by extensive clinical safety data, toxicology data, and clinical pharmacology data for bempegaldesleukin as described in Sections 2.2.4.1, 2.2.4.2, and 2.2.4.3, respectively.

As an additional measure of caution, the first two patients randomized and treated (1 bempegaldesleukin/SOC and 1 placebo/SOC]) in each dose cohort will serve as sentinel patients. A Cohort Review Committee (CRC) will monitor the 2 sentinel patients for safety and tolerability for the first 72 hours after study drug administration before additional patients are dosed within the same cohort. If the CRC determines additional patients may be randomized, 2 patients will be randomized (1 with bempegaldesleukin/SOC and 1 with placebo/SOC), treated with study drug, and observed for 72 hours. For every 2 patients, the Medical Monitor will review the blinded safety and tolerability data for the first 72 hours after study drug administration to determine if the next 2 patients may be randomized. At the conclusion of each dose level cohort, the CRC will assess the accumulated, blinded safety and tolerability data, as

well as any available PK, pharmacodynamic, and disease measurement data, to assess the benefit/risk profile and determine if dose escalation or de-escalation of bempegaldesleukin at dose levels up to 0.003 mg/kg is warranted.

2.2.4.1 Summary of Clinical Safety Data

The clinical experience with bempegaldesleukin administered either as monotherapy or in combination with nivolumab in cancer patients has illustrated a predictable safety profile manifesting as either acute infusion-related symptoms or related to the early appearance of the active cytokines 24-48 hours post-dose. These treatment emergent AEs are typically mild to moderate in severity and transient in nature. Hypotension is the most clinically concerning, but can be mitigated by maintaining the hydration status of the patient and by appropriate exclusion criteria. The starting dose, 12-fold lower than the maximally tolerated dose, and the single dose administration utilized in this study, minimize exposure to bempegaldesleukin providing a safety margin and allowing careful consideration of the effects of dose escalation or de-escalation. Additionally, the enrollment of COVID-19 infected patients with mild disease avoids the potential risk of an untoward contribution to the cytokine milieu that complicates the course of more advanced patients.

2.2.4.2 Summary of Toxicology Data

Good Laboratory Practice toxicology studies evaluated the safety of bempegaldesleukin administered every 14 days to Sprague Dawley rats (0.006 to 0.3 mg/kg) and cynomolgus monkeys (0.006, 0.03, and 0.1 mg/kg) for 15 weeks followed by an 8-week recovery period. The no observed adverse effect levels (NOAELs) established in the 15-week studies were 0.1 mg/kg for the rat and 0.03 mg/kg for the monkey. The monkey was identified as the most sensitive species and the starting bempegaldesleukin dose of 0.00075 mg/kg in Study 20-214-34 is 1/40th of the monkey NOAEL of 0.03 mg/kg.

Hypotension is the most clinically significant adverse effect in patients, but similar effects were not observed in monkeys. In spite of this difference, monkeys appeared to have similar sensitivity to humans in responding to the immunostimulatory effects of bempegaldesleukin. Details are provided below.

Treatment with bempegaldesleukin in the 15-week monkey study resulted in a pharmacologically expected, dose-responsive immune stimulation characterized by a cyclic pattern of clinical observations and increases in absolute lymphocyte counts following each dose administration (Table 6). The clinical observations were of minimal severity at the lowest dose tested (0.006 mg/kg), increased with dose level, and were not tolerated at the highest dose tested (0.1 mg/kg).

Bempegaldesleukin-related target organs at the NOAEL dose (0.03 mg/kg) included the gastrointestinal (decreased food consumption, liquid feces), immune (increased lymphocytes; immune cell infiltration and lymphoid organ enlargement), and skin (dry skin, scabs, rash).

Effects in skin and gastrointestinal systems were also noted in clinical trials with bempegaldesleukin. The skin changes observed in the monkey were noted following the fourth dose and therefore, not relevant to the current protocol for COVID-19 since a single dose administration is planned.

At the terminal sacrifice after 15-weeks of dosing, bempegaldesleukin-related microscopic findings at 0.03 mg/kg included minimal to moderate mixed inflammatory cell infiltrates in multiple organs (liver, urinary bladder, heart, adrenal medulla, thyroid, and/or kidney, lung, esophagus, and/or tongue) and immune organ changes (thymus and spleen) consistent with an inflammatory response. All findings were minimal and partially recovered after an 8-week, dose-free period.

Importantly, results from the 15-week monkey study showed that immune stimulation decreased with dose. At the lowest dose of bempegaldesleukin evaluated in the 15-week study, 0.006 mg/kg, minimal inflammatory cell infiltrates were observed and involved fewer tissues (liver, kidney, bladder, heart, and adrenal gland). All findings fully recovered after an 8-week, dose-free period.

As shown in Table 6, the fold change in absolute lymphocyte count was similar in the monkeys (at 0.006 mg/kg) and humans (at 0.003 mg/kg) when plasma exposures are comparable. Therefore, exposure-response for immunological effects was similar in monkeys and humans. A comparable degree of immune stimulation is expected in humans and monkeys at doses that produce similar plasma exposures. Given this relationship, the degree of immune stimulation observed in monkeys at 0.006 mg/kg is expected to be similar to the degree of immune stimulation in patients at the starting dose of 0.00075 mg/kg in Study 20-14-34 is expected to be lower than that observed in monkeys at 0.006 mg/kg. As 0.006 mg/kg had minimal immunologic effects in the 15-week monkey study, the exposure-response data indicate a low risk of hyperinflammatory responses in patients treated with 0.00075 mg/kg.

Species	Dose (mg/kg)	C _{max} (ng/mL) ^a	AUC (ng h/mL) ^a	AUC Ratio: Monkey-to -Human Starting Dose ^b	ALC Maximum Fold Change ^c
	0.1	233	9940	54	5.6
Monkeys	0.03	73	3330	18	3.2
	0.006	15	794	4	2.1
	0.009	43	2190	-	2.6
	0.006	31	1460	-	2.2
Humans	0.003	16	732	-	1.8
-	0.0015	8	366	-	1.5
	0.00075	4	184	-	1.3

Table 6:Bempegaldesleukin Plasma Exposures and Increases Absolute
Lymphocyte Counts in Monkeys and Patients with Cancer

Abbreviation: ALC=absolute lymphocyte count; AUC =area under the concentration-time curve

[figure not shown]
a. C_{max} and AUC are reported for NKTR-214-AC and values for monkeys were measured in Study LS-2017-033 (Day 1) and for humans were predicted (Table 7).

b. AUC Ratio: Monkey AUC at each dose level divided by human AUC at 0.00075 mg/kg

c. ALC Maximum values reported in monkeys (means; LS-2017-033) and in humans (medians) and are changes from baseline after the first dose of bempegaldesleukin.

Dose-related effects of bempegaldesleukin on C-reactive protein were well described in a single-dose toxicity study in monkey. As illustrated in Figure 7, transient increases in C-reactive protein were observed in the mid- and high-dose groups (0.03 and 0.1 mg/kg) during the first week after administration, with peak concentrations occurring on Days 3-4 (2-3 Days post-dose). In the low-dose group, 0.01 mg/kg, changes in C-reactive protein were minimal and only slightly higher than in the vehicle control. C-reactive protein was not evaluated in prior clinical studies of bempegaldesleukin. As plasma exposures with the 0.03 mg/kg dose in monkeys were more than 3-times higher than those predicted in patients over the range of doses in Study 20-214-34 (0.00075 to 0.003 mg/kg), bempegaldesleukin-related increases in C-reactive protein are not expected in this clinical study.

Figure 7:C-Reactive Protein Levels after Bempegaldesleukin Administration in
Female Cynomolgus Monkeys (n=3)

Note: CRP = C-reactive protein; NKTR-214 = bempegaldesleukin Source: A single dose bempegaldesleukin study in the cynomolgus monkey (LS-2012-002)

In summary, safety margins based on plasma exposures at the NOAEL dose in monkeys indicate an 18-fold area under the concentration-time curve (AUC) safety margin for the 0.00075 mg/kg starting dose in Study 20-214-34. In addition, the dose-relatedness of immune stimulation in the 15-week monkey study and calculated monkey-to-human exposure margins support that a low (0.00075 mg/kg), single dose of bempegaldesleukin is unlikely to result in a hyperinflammatory response in humans.

2.2.4.3 Summary of Clinical Pharmacokinetic/Pharmacodynamic Data

Prior clinical studies evaluated bempegaldesleukin in patients with advanced cancer at doses ranging from 0.003 to 0.012 mg/kg. A lower dose range was postulated to result in a favorable benefit risk profile in patients with mild COVID-19. Therefore, PK/PD modeling and dose-response evaluations were used to predict clinical effects at doses ≤ 0.003 mg/kg.

As bempegaldesleukin is being explored as a possible treatment strategy for increasing lymphocyte counts in patients with COVID-19, an endpoint of interest is the change in lymphocytes before and after treatment with bempegaldesleukin. This is quantified by measuring the fold change from baseline (ie, predose Day 1) absolute lymphocyte count to the maximal absolute lymphocyte count between Day 6 and Day 8. A PK/PD model was developed using data from Study 15-214-01 (EXCEL) in which bempegaldesleukin monotherapy was administered to cancer patients at doses of 0.003 mg/kg (N=4), 0.006 mg/kg (N=11), 0.009 mg/kg (N=5), and 0.012 mg/kg (N=1). The model predicted median absolute lymphocyte count changes of approximately 1.77-, 2.20-, and 2.6-fold for doses of 0.003, 0.006, and 0.009 mg/kg, respectively, which well described the observed changes within this dose range (Figure 4 and Table 3). The model also predicted median absolute lymphocyte count changes of

approximately1.32- and 1.49-fold for doses of 0.00075 and 0.0015 mg/kg, respectively. This suggests that the planned doses for Study 20-214-34, 0.00075, 0.0015, and 0.003 mg/kg are pharmacologically active.

Dose-response assessments were performed for 15 inflammatory cytokines to evaluate if bempegaldesleukin doses ≤ 0.003 mg/kg could cause hyperinflammation in patients with mild COVID-19. Data from cancer patients in Study 15-214-01 (EXCEL; bempegaldesleukin monotherapy) were evaluated for each of the cytokines shown in Table 7. Plasma concentrations were mostly below the limit of quantification for the following: granulocyte-macrophage colony-stimulating factor (GM-CSF), interferon γ (IFN- γ), IL-3, IL-4, IL-7, and tumor necrosis factor β (TNF- β). Therefore, circulating levels of these 6 cytokines did not appear to be affected by bempegaldesleukin from 0.003 to 0.009 mg/kg. The results for the 9 remaining cvtokines showed that increases in circulating cytokines generally occurred from day 3 to day 7 postdose, coinciding with the pharmacokinetic time course of bempegaldesleukin-related active cytokines (NKTR-214-AC). The percentage of plasma samples with measurable concentrations tended to increase with dose, suggesting dose-response relationships for IL-5, IL-6, IL-8, IL-10, IL-18, macrophage inflammatory protein 1α (MIP- 1α), MIP- 1β , monocyte chemotactic protein 1 (MCP-1), and TNF- α over the bempegaldesleukin dose range of 0.003 to 0.009 mg/kg. These dose-response relationships provide some assurance that any risks associated with bempegaldesleukin induced cytokines may be mitigated by using a low range of doses (0.00075 to 0.003 mg/kg).

A final analysis evaluated biomarkers of possible relevance to the risk of hyperinflammation, where the magnitude of response was evaluated at the highest planned dose in Study 20-214-34. 0.003 mg/kg. This analysis included the following biomarkers in plasma: monocytes, neutrophils, IL-6, and TNF- α . As illustrated in Figure 8, 0.003 mg/kg was not associated with meaningful changes in plasma levels of monocytes or neutrophils. As shown in Table 7, IL-6 concentrations were below the limit of quantification in approximately half of the plasma samples from patients treated at 0.003 mg/kg. Based on data from the remaining plasma samples from this cohort, levels of IL-6 increased no more than 2-fold in 3 of 4 patients treated with bempegaldesleukin at 0.003 mg/kg. In the fourth patient treated at 0.003 mg/kg, IL-6 levels showed a 4- to 6-fold increase on Days 2 to 3 postdose. Maximum IL-6 levels after one dose of 0.003 mg/kg of bempegaldesleukin ranged from < 6.8 to 41 ng/mL. It is difficult to interpret the significance of this transient increase in IL-6 because high statistical heterogeneity has been encountered comparing IL-6 levels between patients with complicated and non-complicated COVID-19 disease (Coomes 2020 [preprint]). Circulating TNF- α did not appear to be affected by 0.003 mg/kg bempegaldesleukin to a meaningful extent, as plasma concentrations of TNF- α were quantifiable in only 25% of the plasma samples from patients treated with 0.003 mg/kg (Table 7).

Taken together, the results of PK/PD modeling, dose-response assessments, and evaluation of biomarkers at the planned highest dose of 0.003 mg/kg show that bempegaldesleukin doses over

the range of 0.00075 to 0.003 mg/kg have the potential to be pharmacologically active with a low risk of inducing hyperinflammation in patients enrolled in Study 20-214-34.

Table 7:Cytokine Determinations in Plasma Samples from Patients Treated
with Bempegaldesleukin (Study 15-214-01 [EXCEL])

			GM-CSF	IFN-y	IL-3	IL-4	IL-5	IL-6	L-II	8-1I	IL-10	IL-18	MIP-1α	β1-91Μ	MCP-1	TNF-α	TNF-B
LLOQ) (pg/1	nL) ^a	26	6.8	8.6	43	6	6.8	41	6.1	8.1	42	48	59	83	24	58
Dose ^b	N	n		% of Tested Samples with Measurable Concentrations													
0.003	4	40	0	0	0	0	33	45	0	70	35	75	13	75	75	25	0
0.006	15	143	0	1.4	0	0	42	59	0.7	6 9	48	100	29	90	97	22	0
0.009	6	54	0	5.6	0	5.6	43	70	3.7	59	50	100	39	96	98	30	0

[figure not shown]
Abbreviations: GM-CSF = granulocyte-macrophage colony-stimulating factor; IFN = interferon; IL = interleukin; LLOQ = lower limit of quantitation; MCP = monocyte chemotactic protein; MIP = macrophage inflammatory protein; N = the number of patients; n = the approximate number of samples evaluated in the multiplex cytokine assay; TNF = tumor necrosis factor

a. IL-3 concentrations are in ng/mL.

b. Doses are reported in units of mg/kg.

Source: Study 15-214-01 (EXCEL)

Figure 8: Monocyte and Neutrophil Profiles (Mean + SD) after Administration of 0.003 mg/kg Bempegaldesleukin (Study 15-214-01 [EXCEL])

Shaded areas indicated reference range for central laboratory. Source: Study 15-214-01 (EXCEL)

2.3 Cohort Review Committee

In addition to routine safety monitoring and pharmacovigilance activities, a Cohort Review Committee (CRC, see Section 7.16) will be formed to review safety and tolerability data throughout the study. Specifically, the CRC will perform the following evaluations:

- Monitor the blinded safety and tolerability data for the first 72 hours after study drug administration from the first two sentinel patients randomized (1 patient receiving bempegaldesleukin/SOC and 1 patient receiving placebo/SOC) and treated to determine if additional patients may be enrolled in the dose cohort. If the CRC determines additional patients may be randomized, 2 patients will be randomized (1 with bempegaldesleukin/SOC and 1 with placebo/SOC), treated with study drug, and observed for 72 hours. For every 2 patients, the Medical Monitor will review the blinded safety and tolerability data for the first 72 hours after study drug administration to determine if the next 2 patients may be randomized. If it is not possible to assess the protocol-defined DLT criteria (see Section 5.3.2.1.1), the Medical Monitor will request a review of the safety data by the CRC. It may be necessary for the CRC to review unblinded data in accordance with Nektar Therapeutics internal procedures for unblinding.
- 2. Adjudicate reports of Grade 3 dose-limiting toxicities to determine if they meet the protocol-defined criteria for a DLT and demonstrate evidence indicating at least a possible relationship to study drug in patients confirmed to have received bempegaldesleukin. If it is not possible to assess the protocol-defined DLT criteria (see Section 5.3.2.1.1), the CRC may review unblinded data in accordance with Nektar Therapeutics internal procedures for unblinding.
- 3. At the conclusion of each dose level cohort, assess the accumulated, blinded safety and tolerability data, as well as any available PK, pharmacodynamic, and disease measurement data, to determine if dose escalation or de-escalation is warranted. If it is not possible to assess the protocol-defined DLT criteria (see Section 5.3.2.1.1) for the entire cohort to determine dose escalation, the CRC may review unblinded data in accordance with Nektar Therapeutics internal procedures for unblinding.
- 4. The CRC will also establish the RP2D.

All instances of patient unblinding will be performed in accordance with Nektar Therapeutics' internal procedures for unblinding and associated documentation.

The CRC will also meet on an ad hoc basis, if needed.

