	Medical Monitor reviews blinded safety and tolerability data for the first 72 hours after study drug administration to determine if Patients 9 and 10 can be randomized. ^a
Patients 9 and 10	Randomize Patients 9 and 10 if Medical Monitor approves.
	After 10 patients receive study drug and a 7-day observation period has elapsed, CRC review to determine if dose escalation or de-escalation from the tested bempegaldesleukin dose level can proceed.

a. If it is not possible to assess the protocol-defined DLT criteria (see Section 5.3.2.1.1), the Medical Monitor will request a review of the safety data by the CRC.

The CRC will decide the following:

- Continued dosing of additional patients after the first 2 sentinel patients in a new cohort are treated and a 72-hour safety review period has elapsed. If it is not possible to assess the protocol-defined DLT criteria (see Section 5.3.2.1.1), the CRC may review unblinded data in accordance with Nektar Therapeutics internal procedures for unblinding.
- If reports of Grade 3 dose-limiting toxicities meet the protocol-defined criteria for a DLT and demonstrate evidence indicating at least a possible relationship to study drug in patients confirmed to have received bempegaldesleukin. If it is not possible to assess the protocol-defined DLT criteria (see Section 5.3.2.1.1), the CRC may review unblinded data in accordance with Nektar Therapeutics internal procedures for unblinding.
- Whether dose escalation or de-escalation from the tested bempegaldesleukin dose level can proceed after 10 patients are treated in a dose cohort and a 7-day observation period has elapsed. The CRC decision will be based on the accumulated, blinded safety and tolerability data, as well as any available pharmacokinetic, pharmacodynamic, and disease measurement data. If it is not possible to assess the protocol-defined DLT criteria (see Section 5.3.2.1.1) for the entire cohort to determine dose escalation, the CRC may review unblinded data in accordance with Nektar Therapeutics internal procedures for unblinding.

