5.3.1 Rules for Dose Finding

The DLT evaluation period will be a minimum of 1 week (7 days) (see Section 5.3.2.1).

Patients will be randomized (1:1 ratio) in groups of at least 10 patients (5 bempegaldesleukin/SOC and 5 placebo/SOC) in each dose cohort unless unacceptable toxicity is observed.

Unblinding patient treatment assignment, if required, for the purpose of dose-limiting toxicity (DLT) adjudication will be performed in accordance with Nektar Therapeutics internal procedures for unblinding and associated documentation.

The definition of a DLT is provided in Section 5.3.2.1. If no DLTs occur in a cohort of at least 5 patients who received bempegaldesleukin, a new cohort of 10 patients may be randomized and treated at the next higher dose level (Table 8). If only 1 of the 5 patients who received bempegaldesleukin in a dose cohort experiences a CRC-confirmed DLT, then the next cohort of 10 patients may be treated at the next higher dose level. If 2 or more patients who received bempegaldesleukin within a cohort experience CRC-confirmed DLTs, then that dose level will be above the MTD (the highest dose tested where no more than 1 of 5 patients who received bempegaldesleukin has experienced a CRC-confirmed DLT). If 10 patients have already been enrolled into a cohort and additional patients have signed the ICF and are undergoing the screening process, they may be enrolled to the cohort with Sponsor approval; however, these patients are not required to be included in the dose escalation or de-escalation decision for that cohort.

Approximately 30 patients will be enrolled.

5.3.2 **Dose-Limiting Toxicities (DLTs)**

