5.3.2.1.1 DLTs Related to Study Drug

AEs related to study drug(s) that will be defined as a DLT include the following:

- Any Grade \geq 3 drug-related AE.
- Any Grade ≥ 3 drug-related laboratory abnormality that is clinically significant per the Investigator.
- Respiratory compromise or other virus-related AE attributed to worsening COVID-19, such as severe hypoxia, cyanosis, or chest pain/pressure.

All AEs that meet DLT criteria must be recorded in the electronic data capture system within approximately 24 hours of awareness.

Each AE reported as related to study drug that meet any of the above definitions will be adjudicated by the CRC. If the event is confirmed to be at least possibly related to study drug, meets any of the above definitions, and is confirmed to have occurred in a patient treated with bempegaldesleukin, the event will be considered to be a DLT.

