5.14 Blinding

The Investigator, the patients, and all study site and Nektar personnel involved in study activities other than those involved in dispensing the study drugs must remain blinded to each patient's treatment assignment.

In circumstances when knowledge about the study drug received is required to adequately manage serious side effects or AEs experienced by the patient, for expedited reporting of SAEs

to the regulatory authorities or evaluation of severe AEs per the stopping rules described in Section 5.6.2 it may be necessary to unblind a patient's treatment regimen before all outcome assessments have been performed. If the Investigator believes that the study blind needs to be broken for a patient, the Investigator must contact the Nektar Medical Monitor. Unblinding will follow Nektar Therapeutics' internal procedures for unblinding and associated documentation. If the blind is broken, details surrounding the breaking of the blind (eg, date, time, and reason) are to be recorded in the patient's study file.

Bempegaldesleukin will be supplied open label to the clinical site.

An unblinded pharmacist not involved in any other aspect of the study conduct will be designated to manage and account for bempegaldesleukin, and to prepare the bempegaldesleukin or placebo dosing solution for blinded administration to each patient. The pharmacist will ensure that all other study personnel and patients remain blinded to treatment assignment. Study drug accountability for each dose cohort will also be performed by an unblinded monitor not otherwise associated with the day to day operational conduct of the study.

In the course of DLT adjudication, if it is not possible to assess the protocol-defined DLT criteria (see Section 5.3.2.1.1), the CRC may review unblinded data in accordance with Nektar Therapeutics internal procedures for unblinding. Additionally, after 10 patients in a dose cohort have completed a 7-day observation period, if it is not possible to assess the protocol-defined DLT criteria for the entire cohort (see Section 5.3.2.1.1), the CRC may review unblinded data in accordance with Nektar Therapeutics internal procedures for unblinding to characterize the safety profile of bempegaldesleukin relative to placebo treatment to determine if dose escalation or de-escalation is warranted.

Unblinding of patient treatment assignment will follow Nektar Therapeutics' internal procedures for unblinding and associated documentation.

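### The CRC's DLT causality call is not required to be recorded before treatment is known, and the placebo DLT count planned in SAP 11.1 is zero by definition

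*Protocol*

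**What the plan says.** **The CRC's task.** Protocol Section 2.3 (item 2) has the CRC adjudicate whether reported toxicities meet the DLT criteria and "demonstrate evidence indicating at least a possible relationship to study drug in patients confirmed to have received bempegaldesleukin". Section 5.3 repeats the task in nearly the same words.

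**The DLT definition.** Section 5.3.2.1.1 sends to the CRC events that were reported as related and fit a listed type. One listed type is "Respiratory compromise or other virus-related AE attributed to worsening COVID-19, such as severe hypoxia, cyanosis, or chest pain/pressure". It then sets three conditions: the event is at least possibly related, it meets a definition, and it "is confirmed to have occurred in a patient treated with bempegaldesleukin, the event will be considered to be a DLT".

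**Unblinding.** Section 2.3 states: "If it is not possible to assess the protocol-defined DLT criteria (see Section 5.3.2.1.1), the CRC may review unblinded data". On access to such data during adjudication, Section 5.14 says: "In the course of DLT adjudication, if it is not possible to assess the protocol-defined DLT criteria (see Section 5.3.2.1.1), the CRC may review unblinded". Section 5.15 staggers dosing in pairs of one active and one placebo patient.

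**Use of the count.** Section 5.3.1 states: "If 2 or more patients who received bempegaldesleukin within a cohort experience CRC-confirmed DLTs, then that dose level will be above the MTD". The pause rule in Section 5.4 also counts only adjudicated events in patients who actually received bempegaldesleukin.

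**Reporting.** SAP 11.1 plans the number and percentage of patients with any DLT for each dose level and for placebo. SAP 5.0 pools placebo into one group.

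**The concern.** Section 2.2.1 gives the purpose of the placebo control as "To objectively assess the safety and disease measurement of bempegaldesleukin treatment for adults with mild COVID-19". Worsening COVID-19 is a listed DLT type, and COVID-19 itself causes such events. Under Section 7.4, an event reasonably explained by the underlying disease is not related. These are therefore hard cases to attribute, and plausibly among those in which the CRC would ask to see treatment.

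Only CRC-confirmed events count toward the MTD. If the CRC settles relatedness with the arm in view, an ambiguous event in an active patient is judged by someone who knows the drug was given. The same event in a placebo patient needs no judgement, because it cannot be a DLT. The count behind the MTD could then shift. The placebo arm would also supply no adjudicated count of like events to set beside it.

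**Working it through.** **1. Order of the steps**

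- Sections 2.3 (item 2) and 5.3 word the relatedness judgement as one about patients confirmed to be on drug. This can describe a sequence, or only the conditions for a final DLT.
- Section 5.3.2.1.1 lists relatedness, then criteria, then treatment, without saying that the list is a sequence.
- Sections 2.3, 5.3 and 5.14 allow unblinding within adjudication. None asks for a recorded blinded assessment first.
- Section 5.15: in a complete pair, opening one patient fixes the partner's arm.

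Result: the order is unspecified, and the causality call has no stated protection from knowledge of the arm.

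**2. Where blinding does hold**

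Section 5.14 keeps Investigators blinded. Section 7.4 has them judge relatedness for bempegaldesleukin or placebo alike. Referral to the CRC therefore works the same way in both arms, and the exposure is limited to the CRC's second-level decision.

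**3. The placebo DLT count**

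Planned numbers: 3 cohorts × 10 = 30 patients, matching the stated total of about 30, with 3 × 5 = 15 on placebo. Under Section 5.3.2.1.1 a placebo patient cannot have a DLT, so SAP 11.1 must show 0 of 15 whatever happens. Read as data, 0/15 would give a two-sided 95% upper limit of 1 − 0.025^(1/15) = 21.8%. That bound would mean nothing, because the zero is fixed in advance.

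**4. What the 2-of-5 rule does with background events**

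The documents give no background rate, so the rates here are assumptions. The 14% is the proportion of reported US cases hospitalised (Section 2.1.1.1). It is not a 7-day rate in this selected mild population. Assume no drug effect and every background event called related:

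P(X ≥ 2 of 5) = 1 − (1 − p)^5 − 5p(1 − p)^4

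- p = 0.05: 1 − 0.7738 − 0.2036 = 2.3%
- p = 0.10: 1 − 0.5905 − 0.3281 = 8.1%
- p = 0.14: 1 − 0.4704 − 0.3829 = 14.7%

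At least once in three cohorts, 1 − (1 − P)^3: 6.6%, 22.5% and 37.9%.

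**5. Why these figures are not the bias**

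Let b be the background rate and a the share of background events called related, so that p = a × b.

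| a | b = 10% | b = 20% |
|---|---|---|
| 25% | 0.6% | 2.3% |
| 50% | 2.3% | 8.1% |
| 75% | 4.8% | 16.5% |
| 100% | 8.1% | 26.3% |

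The effect of unblinding is the difference between two rows: a with the arm known and a with the arm hidden. If the two are equal, the effect is zero. The documents give neither value.

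**6. What adjudicated placebo data could show**

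With 0 of 5 in one cohort, the two-sided 95% upper limit is 1 − 0.025^(1/5) = 52.2%. With 0 of 15 pooled it is 21.8%. With 3 of 15 the exact 95% interval is 4.3% to 48.1%. This is a coarse background rate, but a real one.

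**The case against.** The strongest reply has five parts.

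- *The definition puts treatment last.* Correct. A reader might infer from Sections 2.3 and 5.3 that the CRC always judges causality after treatment is confirmed. The documents do not establish that. What stands is that the order is open.
- *Blinded Investigators filter events in both arms first.* Correct, and this rules out saying that the plan sets different attribution rules by arm. It does not protect the CRC's own judgement, which decides the count.
- *Placebo events are not lost.* Correct. SAP 11.2 tabulates treatment-emergent events by treatment, including drug-related Grade 3 or higher events and worsening-COVID respiratory events. Section 5.14 also allows an unblinded comparison with placebo, but only when the criteria cannot be assessed for the whole cohort. What placebo patients lack is an adjudicated DLT-type result.
- *Unblinding is discretionary and follows the sponsor's internal procedures.* Those procedures may fix the order. They are not in the documents, and the protocol does not say that they do.
- *Any over-calling errs toward caution.* That holds for over-calling. Knowledge of the arm could also lead to under-calling, and the documents do not settle the direction.

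**Conclusion.** The point holds as a gap in protection against bias, together with a SAP table that cannot do its job. It does not show that the MTD is biased.

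Three things follow from the text. Treatment received is part of the DLT definition. No provision requires the CRC's causality call to be recorded before the arm is known. The placebo entry in SAP 11.1 is zero by construction.

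The size of any bias is not computable: it needs a background rate and two attribution shares, and none of these is given. A reader might take 2.3%, 8.1% and 14.7% per cohort as the harm done by unblinding. They are not. They are properties of an active-only 2-of-5 rule at assumed rates with full attribution, and blinded adjudication with the same attribution would give the same numbers.

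The change is worth making because it costs little and safeguards the judgement on which escalation rests.

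**What to change.** Reconcile Protocol Sections 2.3 (item 2), 5.3, 5.3.2.1.1 and 5.14 to one order for non-emergency adjudication:

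1. For every event referred, in either arm, the CRC records while blinded whether the DLT criteria are met and whether the event is at least possibly related.
2. Only then is treatment read. The existing active-arm count and threshold apply unchanged.
3. If the CRC unblinds because a case cannot be assessed, it first records its blinded assessment, with not assessable as an allowed entry. The blinded and unblinded assessments are both kept.

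In SAP 11.1, report the blinded adjudicated DLT-type events by dose level and for pooled placebo, in place of a placebo DLT count that is zero by definition.

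How cases that remain undecidable should count is for the sponsor to decide. A default of related would raise the active-arm count and should not enter through this change. The emergency and cohort-level unblinding provisions can stay.

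Cost: wording in the protocol, SAP and CRC charter, and one extra recorded field per adjudicated event.
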